8.1 Screening

As per the USM, no further enrollment is allowed.

Written Informed Consent must be obtained before any study specific procedures are performed. During the screening assessment period, inclusion and exclusion criteria will be evaluated and all screening assessments to confirm eligibility must be performed prior to randomization.

For details of assessments required during screening please refer to [Table 8-2](#).

Participants will be required to have all screening assessments within 42 days of randomization with the exception of CAG repeat and height. However, participants may remain in screening for greater than 42 days in the following cases:

- If recruitment (i.e. randomization) is paused (e.g. enrollment is complete for open treatment arms and pending opening of additional treatment arms following the cohort gating assessment),
- In cases where a switch in concomitant medication is considered by the Investigator following the guidance in Table 6-2, participants should be on a stable dose and regimen of permitted chronic concomitant medications for at least 6 weeks prior to receiving the first dose of study drug which in the medical judgement of the Investigator is not anticipated to change during the study. If new medications are initiated during Screening, laboratory evaluations must meet eligibility criteria before first dose of study drug.
- In order to minimize patient burden and upon consultation with the Novartis, the screening period may also be extended beyond 42 days to accommodate the scheduling of baseline assessments.

A participant who has laboratory test results that do not satisfy the entrance criteria may have the tests repeated. These tests may be repeated as soon as the Investigator believes the re-test results are likely to be within the acceptable range to satisfy the entrance criteria, but should be completed within the screening period. In this instance, the participant will not be required to sign another Informed Consent Form (ICF), and the original Participant Number assigned by the Investigator will be used. In the event that the laboratory tests cannot be performed within the screening visit window, or the re-tests do not meet the entrance criteria, or other eligibility criteria have changed and are not met anymore, the participant is considered a screen failure, and must be discontinued from the study.

At this time, participants will be eligible to randomize into any open Treatment Arm if it has not yet been completed.

At that time, and depending on the overall recruitment rate and number of participants in active screening, guidance will be provided to Investigators regarding screening new potential patients.

All visits are to be scheduled according to the appropriate number of calendar days from Day 1 of study drug administration, and not from the previous visit date.

It is permissible to re-screen a participant if she/he fails the initial screening; however, each case must be discussed and agreed with the Novartis on a case-by-case basis.

8.1.1 Information to be collected on screening failures

Participants who sign an informed consent form and are subsequently found to be ineligible, for any reason, prior to randomization will be considered as screen failures. The reason for screen failure should be recorded on the appropriate eCRF. The demographic information, informed consent, and Inclusion/Exclusion pages must also be completed for screen failure participants. No other data will be entered into the clinical database for participants who are screen failures, unless the participant experienced a serious adverse event during the screening period ([Section 10.1.3](#)). If the participant fails to be randomized, the IRT must be notified within 2 days of the screen fail that the participant was not randomized. Data and samples collected from participants prior to screen failure may still be analyzed.

Participants who are randomized and fail to start treatment, e.g. participants randomized in error, will be considered an early terminator. The reason should be recorded on the appropriate eCRF.

8.2 Participant demographics/other baseline characteristics

Country-specific regulations should be considered for the collection of demographic and baseline characteristics in alignment with eCRF.

Participant demographics and baseline characteristics collected will include the following: age of participant, gender (and childbearing potential for female), education level, race and ethnicity, height, weight, smoking and alcohol history, all relevant medical history including HD history, CAG repeat length, (for participants with previously existing source documentation, prior and current concomitant medication. For full list of assessments at screening and BL, please refer to [Table 8-2](#).

BL assessments may be completed over a 6-day period.

Patients should not be randomized and receive study drug treatment until the baseline MRI scan has passed quality control (QC) at central vendor (expected turnaround time 3 days).

The LP should be performed on a different day than both the MRI and HD assessments; however if it cannot be, then the MRI and/or HD assessments must be completed prior to the LP.

8.3 Efficacy/Pharmacodynamics

Efficacy assessments include the following:

- Unified Huntington's Disease Rating Scales (UHDRS) components:
 - Total Functional Capacity (TFC)
 - Total Motor Scale (TMS)
 - Independence Scale (IS)

[REDACTED]

8.3.1 Unified Huntington's Disease Rating Scales (UHDRS)

The UHDRS is a research tool developed by the Huntington Study Group (HSG) to provide a uniform assessment of the clinical features and course of HD. It has undergone extensive reliability and validity testing ([Huntington Study 1996](#)). For this study, the UHDRS components collected will be for total functional capacity, total motor score, independence scale, and the functional assessment score. These components are clinician-guided assessments based on participant interview, physical exam and observation during motor activities.

8.3.1.1 UHDRS Total Functional Capacity (TFC)

The TFC focuses on the Investigator's assessment of the participant's capacity to perform a range of activities of daily living including occupation, finances, self-care, domestic chores and activities of daily living. The responses are derived from interview with the participant and/or companion, if applicable. Scores range from 0 to 13, with higher scores representing better functioning.

8.3.1.2 UHDRS Independence Scale (IS)

The IS represents the Investigator's assessment of the participant's level of independence, including topics of employment, finances, self-care and feeding. The scale has 19 discrete scores, from 10 (tube fed, total bed care) to 100 (no special care needed) with 5 point increments in between.

8.3.1.3 UHDRS Total Motor Scale (TMS)

The TMS is the cumulative sum of the individual motor ratings obtained during the administration of the motor assessment portion of the UHDRS. Scores range from 0 to 124; the higher score represents more significant impairment.

8.3.4 Imaging

Changes in volumetric MRI will be measured in regions of interests. Patients with HD have progressive reduction in volume in brain structures such as, but not limited to, the caudate, putamen, and cerebral cortex and increased ventricular volume (Johnson and Gregory 2019). Striatal atrophy has been the most consistent and sensitive finding in several observational imaging studies and is indicated as the earliest region to show volume loss. Studies have shown significant cross-sectional reductions in caudate and putamen volume up to 15 years prior to disease onset (Paulsen et al 2010) with longitudinal atrophy rates of 3-4% per year (Georgiou-Karistianis et al 2013). In addition, a combination of volume changes significantly correlate with clinical scales and provides an increased effect size and reduced required sample size for detecting a treatment effect based on one-year longitudinal MRI imaging data in patients with HD (Frost et al 2017). Ventricular volume will also be monitored from a safety perspective, to assess if similar increases in lateral ventricular volume occur as was seen with a HTT lowering antisense oligonucleotide (Tabrizi et al 2019b).

Imaging data will be collected, checked for quality, and read centrally as specified in the Imaging Review Charter by an imaging vendor designated by Novartis. Lateral ventricular volume will be assessed and monitored to detect if changes occur during the course of the study. A longitudinal increase in lateral ventricular volume is known to occur with age ($\sim 0.4\text{ml/y}$, $\sim 0.26\%/\text{y}$) and is increased approximately 4-fold in Huntington's disease ($\sim 1.5\text{ml/y}$, $\sim 1\%/\text{y}$) (Hobbs et al 2010).

Patients should not be randomized and receive study drug treatment until the baseline MRI scan has passed quality control (QC) at central vendor (expected turnaround time 3 days).

Three-dimensional MRI data will be acquired and used to measure brain volume at each time point and changes in brain volume longitudinally. Brain MRI scans will be performed at each time point without gadolinium contrast. Additional scan sequences, if feasible at the site, may include diffusion imaging to assess motion features of water and metrics of white matter integrity. Details regarding the MRI scan sequences, methods for assessment and recording are defined in the Imaging Vendor Manuals.

The LP should be performed on a different day than both the MRI and HD assessments; however if it cannot be, then the MRI and/or HD assessments must be completed **prior** to the LP. In the instance that a repeat MRI is needed due to QC issues, the MRI rescan should be acquired 48 h post-LP if there are no associated complication risks noted by the site physician. If there are LP associated complications, it is at the site physicians' discretion to delay the MRI rescan until side-effects resolve.

In the event an MRI cannot be performed after randomization, a local CT may be collected under exceptional circumstances for safety evaluations only, using the site's local imaging

protocol and standard procedures. If no new MRIs can be performed for the remainder of the study, such cases should be discussed with the Novartis on a case by case basis and participant's discontinuation from the study should be considered by the Investigator.

The coded medical images will be used for analysis as described in the imaging review charter; however, the images may also be used for the development and evaluation of new analysis methods directly related to the area of research that this study covers.

Sites will not receive any central read reports nor volumetric data from the central vendor during the study. Images should be locally reviewed by the Investigator for incidental findings. For the purpose of the study only clinically relevant abnormalities noted should be recorded as AE. MRI data will be archived as source documents according to local site practice and regulations.

[REDACTED]

8.3.5 Biomarkers/Pharmacodynamics

As per the USM, PK [REDACTED] including mHTT/HTT (plasma [REDACTED]) [REDACTED] should only be collected in all randomized participants up to 6 weeks after the last dose of study drug.

Mutant Huntingtin (mHTT) protein will be measured in CSF at time points specified in Table 8-2, Table 8-3 and Table 8-4, to evaluate the dose-response relationship between branaplam doses and mHTT in CSF. This relationship will be determined by statistical modelling based on the percent reduction of mHTT observed from BL levels. Total HTT protein will also be measured in CSF at time points specified in Table 8-2, Table 8-3 and Table 8-4. To assess the pharmacodynamic effect of branaplam administered once weekly, mHTT and total HTT will also be measured in plasma [REDACTED] at time points specified in Table 8-2, Table 8-3 and Table 8-4.

[REDACTED]

For visits where [REDACTED] plasma samples are collected only once a day, they must always be collected at approximately the same time of the day.

[REDACTED]

For CSF samples, standard safety assessments performed by the site according to local standard practice may include, but are not limited to, the measurement of cells, glucose and protein. NfL [REDACTED] biomarkers may also be investigated centrally (Section 8.5.3). [REDACTED]

[REDACTED]

Refer to Section 8.5.4.1 for considerations regarding the LP.

8.3.6 Appropriateness of efficacy assessments

Efficacy/PD assessments chosen are standard in HD and the relevance noted in each Section 8.3.5 above.

8.4 Safety/Tolerability

To minimize burden to participants, it is recommended that safety labs/urinalysis are performed only if required for Adverse Events or follow up of an AE. See VES [Table 8-5](#) for list of safety assessments to be performed following the USM.

Safety assessments are specified below with the assessment schedule detailing when each assessment is to be performed.

For details on AE/SAE collection and reporting, refer to [Section 10](#).

Table 8-6 Assessments & Specifications

Assessment	Specification
Physical examination	
A complete physical examination including the examination of general appearance, skin, neck (including thyroid), eyes, ears, nose, throat, lungs, heart, abdomen, back, lymph nodes, extremities, vascular, and neurological will be performed at Screening and Baseline visits. If indicated based on medical history and/or symptoms, rectal, external genitalia, breast, and pelvic exams will be performed.
 
A short physical exam will include vital signs (temperature, blood pressure [SBP and DBP] and pulse) examination of general appearance, head, eyes, ears, nose, throat, neck, skin, lungs, heart and abdomen. Evidence of possible bleeding tendency such as bruises or petechial rash should be noted.
 
Information for all physical examinations must be included in the source documentation at the study site. Clinically relevant findings that are present prior to signing informed consent must be recorded on the appropriate eCRF that captures medical history. Significant findings made after signing informed consent which meet the definition of an Adverse Event must be recorded as an adverse event.

Vital signs	Vital signs include temperature (method of body temperature (i.e. oral) is up to site local practices), BP and pulse measurements. After the participant has been supine for ten minutes, systolic and diastolic blood pressure will be measured three times using an automated validated device, e.g. OMRON, with an appropriately sized cuff. The repeat measurements will be made at 1 - 2 minute intervals. In case the cuff sizes available are not large enough for the participant's arm circumference, a sphygmomanometer with an appropriately sized cuff may be used.
Height and weight	Height and body weight (in indoor clothing, but without shoes) will be measured
Neurological	Neurological examination includes at a minimum the following: mental status, cranial nerves I- XII, motor system, deep tendon reflexes, sensory system including touch and vibration, coordination, gait. In addition, a detailed motor, deep tendon reflexes and sensory system examination will be completed and recorded on the appropriate eCRF at screening and at each visit to monitor for any abnormalities. Nerve conduction studies consisting of tibial CMAP and sural SNAP will be done at screening and during study if indicated clinically.
Cardiac	Full PK profile with digital standard 12-lead triplicate ECGs, PK samples and vital signs at the same time points (vital signs = pulse rate, supine systolic and diastolic blood pressure) will be performed. ECHO with GLS will be performed as per assessment schedule. Specific visits will require fasting prior to pre-dose ECGs as specified in the visit schedule and in Section 8.4.2 .
Ophthalmologic	An ophthalmologic examination without sedation using dilated direct and indirect ophthalmoscopy with scleral indentation if necessary will be performed at the time points defined in the Assessment Schedule by an Ophthalmologist.

8.4.1 Laboratory evaluations

Central laboratories will be used for the analysis of scheduled hematology, biochemistry and other blood specimens collected as part of safety monitoring (as detailed [Table 8-7](#)). Dipstick urinalysis will be performed locally (unless local institution policies dictate otherwise), except

in the case of any out of range parameter on scheduled local urinalysis, when a urine sample will be sent to central laboratory for further analysis. Laboratory values obtained during the Screening phase will be used to assess patient's eligibility. The time windows granted for laboratory evaluations are identical to the corresponding visit time windows for each visit (refer to [Table 8-1](#), [Table 8-2](#), [Table 8-3](#), [Table 8-4](#), and [Table 8-5](#) (post-USM)).

The site does not need to wait for the results of centrally-analyzed laboratory assessments when an immediate clinical decision needs to be made and in those cases locally unscheduled testing may be performed.

Details on the collection, shipment of samples and reporting of results by the central laboratory are provided to Investigators separately.

Clinically significant abnormalities must be recorded as either medical history/current medical conditions or adverse events as appropriate.

Table 8-7 **Laboratory evaluations**

Test Category	Test Name
Chemistry	
Albumin, Alkaline phosphatase, ALT, AST, Gamma-glutamyl-transferase (GGT), Lactate dehydrogenase (LDH), Bicarbonate, Calcium, Magnesium, Chloride, Sodium, Potassium, Phosphate, Creatinine, estimated Glomerular filtration rate (eGFR), Creatine kinase (CK), Total Bilirubin, Total Cholesterol, Low density lipoproteins (LDL), High density lipoproteins (HDL), Total Protein, Triglycerides, Blood Urea Nitrogen (BUN) or Urea, Uric Acid, Amylase, Lipase, Glucose, (fasting and non-fasting), high sensitivity C-reactive protein (CRP), fasting bile acids; glycated hemoglobin (HbA1c) (screening visit only)
 
If the total bilirubin concentration is increased above 1.5 times the upper limit of normal, direct and indirect reacting bilirubin should be differentiated.
 
In the event ALT/AST is above 3 times upper limit of normal, reflex testing will be performed by the central laboratory for GLDH (glutamate dehydrogenase)
 
In the event CK is above ULN then reflex testing of isoenzymes will be performed by the central laboratory
 
In case of severe amylase/lipase elevations (> 2x ULN), a reflex fractionation amylase test is recommended (local testing acceptable)

Hematology	
Hematocrit, Hemoglobin, mean corpuscular hemoglobin (MCH), mean corpuscular hemoglobin concentration (MCHC), mean corpuscular volume (MCV), Platelets, Mean Platelet volume* (MPV), Red blood cells RBC), White blood cells, RBC Morphology, Differential (Basophils, Eosinophils, Lymphocytes, Monocytes, Neutrophils, Bands, Other (absolute value preferred, %s are acceptable), reticulocytes
 
* In event the platelet count is out of range (both upper and lower limits) MPV reflex testing will be performed by the central laboratory

Urinalysis	
Macroscopic Panel (Dipstick) (Color, Bilirubin, Blood, Glucose, Ketones, Leukocytes esterase, Nitrite, pH, Protein, Specific Gravity)
 
Microscopic Panel (Red Blood Cells, White Blood Cells, Casts, Crystals, Bacteria, Epithelial cells); done only if findings on urine dipstick. In addition the central laboratory will perform analysis of the urine protein and blood.

Coagulation	Prothrombin time (PT), International normalized ratio [INR]), Activated partial thromboplastin time (APTT)
Additional tests	FSH, Troponin T, NTproBNP, T3 Triiodothyronine [free], T4 Thyroxine [free], Thyroid-Stimulating Hormone (TSH)
Pregnancy Test	Serum / Urine pregnancy test

8.4.2 Cardiac assessments

Electrocardiogram (ECG)

As per USM: Refer to [Table 8-5 for schedule of ECG assessments. Participants do not require to be fasting prior to the ECG.](#)

ECGs must be recorded after 10 minutes rest in the supine position to ensure a stable BL, according to the ECG Investigator Manual. The Fridericia QT correction formula (QTcF) should be used for clinical decisions.

TriPLICATE 12-lead resting ECGs are to be collected, with ECG machines as supplied by central ECG vendor, at all timepoints pre-specified in the visit and assessment schedule and should be performed with a 2-4 minutes interval between each ECG. Details on the triplicate ECG collection procedure and its specific requirements and restrictions for the participant are provided in an ECG Investigator Manual. Specific visits will require fasting prior to pre-dose ECGs as specified in [Table 8-8](#), and in [Section 6.7.2](#). For PK sampling timepoints, please see [Appendix 16.3](#).

Table 8-8 Central ECG Collection Plan

Period	Visit Name	Days	Timepoint	Timing of Triplicate ECGs
Screening	Screening	-42 to -7	-	Anytime
Baseline	Baseline	-6 to -1	-	Anytime
DRF	Wk 1	1	0 hr	Pre-dose after 4 hr fasting
DRF	Wk 1	1	4 hr	Post-dose
DRF	Wk 1	1	12 hr	Post-dose after 4 hr fasting
DRF	Wk 2	8	-	Pre-dose
DRF	Wk 3	15	-	Pre-dose
DRF	Wk 5	29	-	Pre-dose
DRF	Wk 9	57	0 hr	Pre-dose after 4 hr fasting
DRF	Wk 9	57	4 hr	Post-dose
DRF	Wk 9	57	12 hr	Post-dose after 4 hr fasting
DRF	Wk 13	85	-	Pre-dose
DRF	Wk 17	113	0	Pre-dose
BE & OLE	Wk 21 until EOT OLE	141 to EOT OLE	-	Pre-dose

For any ECGs with participant safety concerns, the Investigator should treat based on standard of care.

In the event that a clinically significant ECG abnormality is identified at the site at the time of ECG collection (e.g. severe arrhythmia, conduction abnormality of QTcF >500 msec), an expedited review by the central reader may be requested if applicable, and the ECG should be repeated to confirm the diagnosis. If the participant is hemodynamically compromised, the Investigator or a medically qualified person must initiate appropriate safety procedures without delay (for example cardioversion).

Clinically significant abnormalities must be recorded on the eCRF as either medical history/current medical conditions or adverse events as appropriate.

Echocardiogram with Global Longitudinal Strain (GLS)

Echocardiogram with GLS is no longer required per the USM follow-up notification dated 06-Dec-2022.

Pre-USM: Echocardiogram with GLS will be performed per the assessment schedule. An echocardiogram is a test that uses high frequency sound waves (ultrasound) to make a cardiac image and provides information regarding cardiac structure and function. GLS is an additional parameter used to assess myocardial contractility.

Two dimensional echocardiography measurements will be assessed during the study. The images will be transmitted to a central reading vendor for independent review. Sites will receive appropriate training as well as an Echocardiography Manual that includes detailed instructions and data transfer procedures.

A Left Ventricular Ejection Fraction (LVEF) $<50\%$ (calculated using the biplane Simpson method) is considered reduced and clinically relevant. Reductions in LVEF $\geq 10\%$ units and/or GLS $\geq 15\%$ units change from baseline are considered clinically relevant following consensus guidelines for abnormal cardiac response ([Plana et al 2014](#)).

Echocardiograms should be locally reviewed by the Investigator for incidental findings. For the purpose of the study only clinically relevant abnormalities noted should be recorded as AE. All other echocardiography assessments will be done by central reading vendor. The central reading vendor will only send alert notifications to sites when the LVEF and GLS thresholds defined above are met.

Eligibility at screening will be confirmed by the Investigator based on the local echocardiography assessment as reported by a cardiologist. Recordings at screening will be sent to the central reader to serve as reference measurement for future comparison. All recordings will be sent to the central reader.

Aligned with recommendations of the American Society of Echocardiography concerning the use of echocardiography in clinical trials ([Gottdiener et al 2004](#)), the following standard parameters - pertinent to the assessment of changes in cardiac muscle mass and/or contractile function - will be monitored during the study:

- Left ventricular wall (anterior and posterior) and septal thickness
- Left ventricular mass and mass index
- Left ventricular end-diastolic volume
- Left ventricular end-systolic volume
- Left ventricular ejection fraction
- Left ventricular diastolic and systolic diameter
- Left atrial size and volume
- Left Ventricular Global Longitudinal Strain

Cardiac Enzymes

Troponin and NTproBNP levels will be assessed at BL and timepoints outlined in the assessment schedule. These blood tests are to monitor cardiac injury and cardiac failure.

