No heart functional changes were observed in the dog safety pharmacology study or in the 6 weeks monkey study with twice-weekly dosing. The C_{max} at the highest dose in the monkey (436 ng/mL) were 4.5-fold higher compared to C_{max} observed in Type 1 SMA patients and 3.3-fold higher compared to predicted C_{max} at the highest dose of this study.

Microscopic findings (cardiomyocyte vacuolation) were observed only in one mouse study. The species specificity and mechanism underlying this finding will be further explored.

In the 4 week wild type RasH2 mouse dose-range finding study with daily administration of 10, 30, and 60 mg/kg/day of branaplam, histological findings of vacuolation of cardiomyocytes were noted. The estimated AUC_{week} at the highest dose in male and female mice without heart findings (4 mg/kg/day) was about 9345 h*ng/mL being approximately 3-fold and 0.86-fold higher than the predicted AUC_{week} at the starting and highest dose of this study, respectively. The heart was not identified as a target organ in previous animal safety studies in rat and dog with daily administration of branaplam up to 2.5 and 2 mg/kg/day in rat and dog, respectively. No heart findings were observed in a 6-week monkey study with twice weekly branaplam dosing up to 6 mg/kg/dose.

In the ongoing study CLMI070X2201 in Type 1 SMA patients there have been 3 cardiovascular Suspected Unexpected Serious Adverse Reactions (SUSARs) reported in 3 patients, PTs were left ventricular hypertrophy and hypertension in one patient and PTs sinus tachycardia and left ventricular dysfunction in one patient and pericardial effusion in one patient. Overall, the majority of TEAEs in the cardiac and vascular disorders were Grade 1 and 2 and resolved on treatment. There were no clinically meaningful changes in any of the ECG parameters (PR, RR, QRS, QT, QTcB, and QTcF).

In the SAD study in healthy subjects no abnormalities of clinical relevance and no trends were observed in standard safety electrocardiograms and no relevant arrhythmia events were detected in the 25-hour Holter ECG-based arrhythmia analysis in any of the subjects. Vital signs assessments did not show any abnormalities or trends of clinical relevance. Orthostatic vital signs assessment (supine and standing SBP, DBP and pulse rate) did not reveal any signs of orthostatic dysregulation/postural hypotension, except for 1 subject in the 420-mg group.

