12.5.2 Safety endpoints

As per the USM, the OLE period is no longer applicable. Safety analyses will be carried out based on the SAF cumulatively.

As one of the primary endpoint, safety analyses will be carried out based on the SAF for summaries including Core Period data, OLSAF for summaries using only OLE data:

- IA: all safety data from baseline to a cut-off date (a date pre-specified for iDBL) will be reviewed by treatment group.
- End of study: all safety data will be reported cumulatively (Core + OLE) and by two periods separately:
 1. Core period (DRF + BE: this would partially overlap with IA, plus the data from BE that were not reported at IA) by treatment group
 2. OLE period by treatment group (only if more than one dose is selected for OLE) and by treatment group originally assigned in the core period

Adverse events

The number (and percentage) of participants with treatment emergent AEs will be summarized in the following ways:

- By primary system organ class and preferred term.
- By primary system organ class, preferred term and maximum severity.
- By Standardized MedDRA Query (SMQ) and preferred term.

Separate summaries will be provided for SAEs, deaths, and study medication related AEs, AEs leading to study discontinuation and AEs leading to study drug interruption/discontinuation.

Vital signs

Number and percentage of participants with clinically notable vital signs will be presented. Participants with clinically notable vital signs will be defined in the SAP.

Cardiac assessments

Cardiac assessments will include 12-lead ECG, Echocardiogram (ECHO) with GLS, and cardiac enzymes (Troponin and NTproBNP). For each assessment, summary statistics will be

provided for each individual parameter, as appropriate. Number and percentage of participants with clinically significant abnormalities will be calculated.

Clinical laboratory evaluations

The number and percentage of patients with newly occurring or worsening laboratory abnormalities meeting the clinically notable criteria (to be defined in the SAP) will be summarized by laboratory parameter. The most extreme post-dose value is considered. For selected laboratory tests (e.g., liver enzyme abnormalities), summary statistics of change from BL laboratory results will be presented by laboratory test category, visit and treatment group.

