##### Summary tables

Descriptive statistics will be summarized for the following parameters by visit:

- Left ventricular ejection fraction (LVEF)
- Left Ventricular Global Longitudinal Strain (LVGLS)

The number and percentage of participants with clinically notable values at any post baseline visits will be summarized by period, parameters. The clinically notable are defined in [Appendix 5.5](#).

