##### Listings

---

Echocardiogram data will be listed for the participants with clinically notable values.

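### Left ventricular mass and wall thickness are monitored by echocardiogram but have no SAP summary, so hypertrophy with preserved LVEF would appear in no echo table or listing

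*Protocol*

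**What the plan says.** Protocol Section 8.4.2 sends all echocardiogram recordings to a central reader and gives eight items "pertinent to the assessment of changes in cardiac muscle mass and/or contractile function - will be monitored during the study". Two of them measure muscle mass: "Left ventricular wall (anterior and posterior) and septal thickness" and "Left ventricular mass and mass index". The other six are end-diastolic volume, end-systolic volume, LVEF, LV diameters, left atrial size and volume, and GLS.

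Protocol Section 12.5.2 names echocardiogram with GLS among the cardiac assessments and says summary statistics will be "provided for each individual parameter, as appropriate". After the urgent safety measure, Protocol Section 2 still commits to a descriptive summary of all safety data collected in the core period.

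SAP Section 2.7.4.1 uses central results. Its echo table opens with "Descriptive statistics will be summarized for the following parameters by visit" and names LVEF and LVGLS only. A second table counts participants with notable values. The listing rule is "Echocardiogram data will be listed for the participants with clinically notable values". SAP Table 5-14 has one criterion, for LVEF. SAP Section 4, on changes to protocol-specified analyses, gives no reason for leaving the other items out.

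**The concern.** Both tabulated measures describe contractile function. Neither shows whether the muscle has thickened. A participant's LV mass can rise while LVEF stays above its threshold, and the planned echo outputs would not show it.

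This matters for this drug. Protocol Section 4.5 names cardiovascular effects as a potential risk. It reports three cardiovascular SUSARs in three patients of the Type 1 SMA study, of which the "PTs were left ventricular hypertrophy and hypertension in one patient". It also reports cardiomyocyte vacuolation in one mouse study, and it relies on echocardiography as one means of monitoring cardiac risk. Safety is one of the two primary objectives. A report that shows only LVEF and GLS says nothing about cardiac structure, although structural data were collected.

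**Working it through.** The plan gives no figure to reproduce here. The check is a comparison of texts, followed by one short calculation on precision.

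**Coverage of the eight items**

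| Protocol 8.4.2 item | By-visit summary (SAP 2.7.4.1) | Notable criterion (SAP Table 5-14) |
|---|---|---|
| Wall and septal thickness | no | no |
| LV mass and mass index | no | no |
| End-diastolic volume | no | no |
| End-systolic volume | no | no |
| LVEF | yes | yes |
| LV diameters | no | no |
| Left atrial size and volume | no | no |
| GLS | yes | no |

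Two of eight items are summarised, and 8 − 2 = 6 are not. The six include both measures of muscle mass. One of eight has a notable criterion.

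**Following one participant through the outputs.** Suppose LV mass rises markedly and LVEF stays above the threshold.

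1. By-visit table: the participant contributes only LVEF and GLS values.
2. Notable-value table: not counted, because the only criterion is LVEF.
3. Listing: not included, because it is limited to participants with notable values.
4. Adverse events: included only if the site, reviewing locally for incidental findings, judges the change clinically relevant. Under Protocol Section 8.4.2 the central reader alerts sites only on the LVEF and GLS thresholds, so a centrally measured rise in mass need not reach the site.

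If the same participant also had a notable LVEF, step 3 would change. The listing rule does not restrict which echo parameters are printed, so mass and thickness could appear there.

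The LVEF bound in Table 5-14 is printed with a minus sign before the 50%. Taken literally, no value could meet it and the listing would be empty. This may be a typing or PDF-reading artefact, and nothing here rests on it.

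**Precision of a group comparison.** The plan is for about 25 participants in the cohort, allocated 4:1, so about 20 on branaplam and 5 on placebo. Assume all have a baseline and a post-baseline echo, which the documents do not state.

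- SE of the difference in means = SD × √(1/20 + 1/5) = SD × √0.25 = 0.5 SD.
- 95% interval half-width, 23 degrees of freedom: 2.069 × 0.5 SD = 1.03 SD.
- Power for a true 1 SD shift, two-sided 5% t-test: about 48%. With 16 and 4 participants it is about 40%.

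A mean shift of 1 SD would be missed about half the time. The case for reporting these measures therefore rests on individual changes.

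**The case against.** The protocol's commitment is qualified by its as-appropriate wording, and after the safety measure the protocol leaves analysis details to the SAP. The SAP serves an abbreviated report, and echocardiograms were stopped with the notification of 06-Dec-2022. LVEF and GLS are the only echo measures with clinical-relevance thresholds in Protocol Section 8.4.2 and the only echo triggers in Protocol Table 6-3. Limiting listings to participants with notable values is also the SAP's convention for laboratory data, ECG and vital signs. Other cardiac outputs remain: adverse event tables and listings, events of special interest, ECG, troponin and NTproBNP. The hypertrophy report came from a single patient in the Type 1 SMA study, who also had hypertension. The mouse finding was vacuolation in one study; heart findings were absent in the monkey study, and the heart was not a target organ in rat or dog.

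Much of this stands, and it limits how far the point goes. It does not remove the gap. The protocol itself calls these measures pertinent, and its post-termination text keeps the descriptive summary of all safety data. The SAP explains why it drops the HTT biomarkers (assay issues) but not why it drops these. None of the other cardiac outputs reports LV mass or wall thickness.

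Some stronger readings are tempting and are not supported:

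- A reader might infer that hypertrophy cannot show in any echo output. The listing could print mass for a participant with a notable LVEF, and a locally noted, clinically relevant finding would be an adverse event.
- A reader might infer that mass was never examined. The protocol has it monitored and sends the recordings to the central reader; the gap is in reporting.
- A reader might infer that all six unsummarised items must be added. The volumes, diameters and left atrial measures go beyond a concern about muscle mass.

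**Conclusion.** The concern holds in a limited form. LV wall and septal thickness and LV mass and mass index have no summary table and no notable criterion in the SAP, and no reason is given. Hypertrophy with preserved LVEF would appear in no echo table or listing, and its only route into the report as hypertrophy is a site-recorded adverse event. The conclusion rests on reading the SAP's echo table as complete at two parameters and on the central reader's data containing the items the protocol lists.

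This should be corrected, but it threatens no main conclusion of the trial. The human evidence of hypertrophy is one case in another population, and the group comparison would be imprecise (SE about 0.5 SD with about 20 and 5 participants). The figures do not support a claim that a 1 SD mean shift would be reliably detected.

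**What to change.** In SAP Section 2.7.4.1, add by-visit descriptive statistics of value and change from baseline, by treatment group, for LV wall and septal thickness and for LV mass and mass index. List the individual values of these measures for participants with a post-baseline echocardiogram, so that large changes can be seen whatever the LVEF. If the sponsor prefers not to report them, SAP Section 4 should state the omission and the reason.

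The data come from the existing central-reader dataset, so nothing new is collected. The cost is a few more table rows and a somewhat longer listing in an abbreviated report.
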